3. TRIAL DESIGN

3.1. PRIMARY EFFICACY ENDPOINTS

Comparison of mean [REDACTED] Severity Assessment Score between the KPI-121 0.25% ophthalmic suspension group and the vehicle group:

- Visit 4 (based on the mean score for the 3 days prior to Visit 4)

Comparison of mean posterior lid margin hyperemia [REDACTED]

[REDACTED] at Visit 2 between the KPI-121 0.25% ophthalmic suspension group and the vehicle group:

- Visit 4

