3.5. DESCRIPTION OF TRIAL DESIGN

This is a Phase 2, multi-center, double-masked, randomized, vehicle-controlled, parallel-group study designed to evaluate the safety and efficacy of KPI-121 0.25% ophthalmic suspension in subjects with inflammatory MGD.

This study will include up to 6 clinic visits, including 2 weeks of single-masked vehicle run-in followed by up to 30 days of investigational product dosing (KPI-121 0.25% ophthalmic suspension or vehicle).

Up to 750 subjects at up to 12 centers located in the United States (US) will be screened at Visit 1 (Screening). Subject meeting eligibility criteria will enter a 14-day run-in period of QID dosing (1-2 drops per eye of single-masked vehicle). Approximately 200 subjects will be randomized to KPI-121 0.25% ophthalmic suspension or vehicle.

At Visit 2, subjects who continue to meet inclusion/exclusion criteria (with the exception of Inclusion Criteria #4 and #7) will be randomized in an approximate 1:1 ratio to either 1) KPI-121 0.25% ophthalmic suspension administered as 1-2 drops in each eye QID for up to 4 weeks or 2) vehicle administered as 1-2 drops in each eye QID for up to 4 weeks.

The study eye will be selected based on the qualification criteria entered into the Interactive Web Response System (IWRS) for stratification at randomization. These scores are based on findings at Visit 1 only. If both eyes qualify for the study, the study eye will be designated as OD. Randomization numbers will be assigned to subjects as they are entered into the IWRS, based on the following 2 stratification criteria:

- Subject's Visit 1 (Day -14) [REDACTED] score [REDACTED]
[REDACTED] AND
- Visit 1 (Day -14) investigator-rated posterior lid margin hyperemia score [REDACTED]

The IWRS will assign masked study kit numbers, and bottles of investigational product will be dispensed at designated visits. The Sponsor, Investigators, and study staff will be masked during the randomization process and throughout the remainder of the study.

Subjects will return to the clinic for complete study evaluations at Visits 4 and 6 (Day 15 \pm 1 day and Day 29 \pm 1 day, respectively). Subjects will also return at Visits 3 and 5 (Day 8 \pm 1 day and Day 22 \pm 1 day, respectively) [REDACTED], evaluate ocular discomfort, and assess concomitant medication use and AEs. Subjects will discontinue dosing and be released from the study at Visit 6 (Day 29 \pm 1 day).

[REDACTED]

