9.1.2. Analysis of Efficacy

The primary analysis population will be the Intent-to-Treat (ITT) population, defined as all subjects randomized, for all analyses [REDACTED]

[REDACTED] A subset of efficacy analyses will be examined for the Efficacy Evaluable (EE) population, the definition of which will be outlined in the Statistical Analysis Plan and finalized prior to unmasking of study data pursuant to clinical data review.

The primary analysis of all ophthalmic efficacy measures will be based on the single study eye for each subject.

[REDACTED] Severity
Assessment Score between the KPI-121 0.25% ophthalmic suspension group and the vehicle group at Visit 4 (based on the mean score for the 3 days prior to Visit 2 and Visit 4); and (2) comparison of mean posterior lid margin hyperemia [REDACTED]

[REDACTED] at Visit 2 between the KPI-121 0.25% ophthalmic suspension group and the vehicle group at Visit 4.

Secondary and exploratory efficacy endpoints will be evaluated as elaborated in [Section 3](#).

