9.2. SAMPLE SIZE ESTIMATION

A sample size of 71 in each group will have 90% power to detect an effect size of █ using a 2-group t-test with a █ 2-sided significance level.

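### No readable text adjusts the co-primary comparisons for the Visit 2 value or the stratification factors, and Sections 3.1 and 9.1.2 disagree on the role of Visit 2

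*Combined protocol and SAP*

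**What the plan says.** - **Endpoints.** Section 3.1 and the synopsis define each co-primary as a comparison of arm means at Visit 4. The symptom score is given as "Visit 4 (based on the mean score for the 3 days prior to Visit 4"). Change from Visit 2 is listed separately, among the exploratory endpoints of Section 3.3.
- **Analysis.** Section 9.1.2 restates the second co-primary as a "comparison of mean posterior lid margin hyperemia" at Visit 4, with a blacked-out qualifier that ends in a reference to Visit 2. It restates the symptom co-primary with the three days before Visit 2 as well as those before Visit 4. The lead-in to this sentence is blacked out. Its readable part names no test, model or covariate.
- **Test.** The only named test is in Section 9.2, where 71 per group gives 90% power "using a 2-group t-test". The effect size and significance level there are blacked out.
- **Stratification.** Section 3.5: "Randomization numbers will be assigned to subjects as they are entered into the IWRS, based on the following 2 stratification criteria". One factor is the Visit 1 lid margin hyperemia score; the name of the other score is blacked out. On the qualifying scores it adds: "These scores are based on findings at Visit 1 only".
- **Visit 2 data.** Section 5.1.2 schedules the investigator-rated signs at Visit 2, after the vehicle run-in. Exploratory change scores use the three-day symptom mean before Visit 2.
- **Decision rule.** Section 9.3 requires both co-primaries to be significant at 0.05 and treats every other p-value as descriptive.

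**The concern.** The trial collects a baseline for each co-primary after run-in and stratifies on two Visit 1 scores. A raw comparison of Visit 4 means uses neither. Two things follow.

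- Stratified allocation removes between-stratum variation from the treatment difference. An unadjusted standard error still counts it, so the test runs below its stated level.
- Stratification uses scores taken before 14 days of vehicle, so it controls Visit 2 levels only partly. A chance difference at Visit 2 adds noise to the Visit 4 difference, which a baseline covariate would remove.

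Because both endpoints must succeed, lost precision on either one can fail the trial. The disagreement between 3.1 and 9.1.2 adds a second problem: from the readable text, the symptom co-primary could be a Visit 4 mean or a change from Visit 2, and these tests have different power.

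**Working it through.** **Inputs from the documents.** 71 per group, 90% power, two-sided t-test (9.2); level 0.05 (9.3); about 200 randomised at about 1:1, so about 100 per arm (synopsis, 1.4, 3.5).

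**Assumptions.** The effect size d is blacked out and is back-solved. The correlation r between Visit 2 and Visit 4 values is not given; 0.3 to 0.7 is used. Strata cut-points are blacked out; a median split is used. Little loss to follow-up.

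**1. The plan's own figure.** With n = 71 per arm and two-sided 0.05, the noncentral t distribution gives 90% power at d = 0.548. At d = 0.55 the exact t-test needs 71 per arm, with power 90.2%. This is consistent with 9.2 but does not confirm it: 71 per arm also fits d = 0.60 at level 0.025.

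**2. Precision.** ANCOVA standard error = unadjusted standard error × √(1 − r²).
- r = 0.3: √0.91 = 0.954
- r = 0.5: √0.75 = 0.866
- r = 0.7: √0.51 = 0.714

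**3. Power per endpoint.** Noncentral t with noncentrality (d/√(1 − r²)) × √(n/2), and one degree of freedom fewer for ANCOVA:

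| d | per arm | unadjusted | r = 0.3 | r = 0.5 | r = 0.7 |
|---|---|---|---|---|---|
| 0.55 | 71 | 90.2% | 92.7% | 96.4% | 99.5% |
| 0.55 | 100 | 97.2% | 98.2% | 99.4% | >99.9% |
| 0.45 | 100 | 88.6% | 91.3% | 95.5% | 99.3% |

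At 100 per arm the gain is about 1 to 3 points if d = 0.55, and about 3 to 11 points if d = 0.45.

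**4. Both endpoints.** Treating them as independent, at d = 0.45 and 100 per arm: 0.886² = 79% unadjusted, 0.955² = 91% with ANCOVA at r = 0.5. Positive correlation between the endpoints would raise both figures.

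**5. True level of an unadjusted test.** Let R² be the share of Visit 4 variance that the strata explain. The level is about 2[1 − Φ(1.96/√(1 − R²))]. A median split of a Visit 1 score with Visit 1 to Visit 4 correlation q explains R² = q² × 2/π:
- q = 0.3: R² = 0.057, level 4.3%
- q = 0.4: R² = 0.102, level 3.9%
- q = 0.5: R² = 0.159, level 3.3%

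Simulation (20,000 runs, 142 subjects, blocks of four within strata) gave 4.3%, 3.8% and 3.4%.

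**6. If 9.1.2 means a change score.** With equal variances, its standard error is √(2(1 − r)) times that of the raw comparison, which is smaller only if r exceeds 0.5. At r = 0.3 the factor is √1.4 = 1.183, and power at 71 per arm and d = 0.55 falls to 78.5%. So a change score is not a safe substitute for ANCOVA.

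**The case against.** A reader might infer that the plan ignores the Visit 2 baseline and prescribes an unadjusted t-test. The documents do not support that. The place in 9.1.2 where a model would be named is blacked out, and 9.1.2 refers to a separate Statistical Analysis Plan that is not in the file. Visit 2 does appear in the readable wording of both co-primaries there. The t-test is the basis of the sample size; sizing on a t-test and analysing with covariates is common practice. A comparison of means names an endpoint and is compatible with adjusted means.

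The size is also easy to overstate. The plan randomises about 200, not 142, and at 100 per arm unadjusted power is already 97% if d is near 0.55. Stratification itself lifts unadjusted power slightly, to about 91 to 92% at 71 per arm in a simulated version of the design. An unadjusted test would be unbiased and conservative, and its standard error already allows for chance imbalance. Section 3.3 reports many measures both as raw means and as changes, but those p-values are declared descriptive, so no change is needed there.

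All of this stands. It narrows the point without removing it. The Visit 2 mentions do not show adjustment: the symptom wording resembles the synopsis wording for the exploratory change score, and the hyperemia qualifier may only select subjects, as the parallel exploratory endpoint does with a Visit 2 grade of at least 1. If it does, fewer than 200 are analysed for that endpoint and the spare power shrinks.

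**Conclusion.** The point holds in limited form, with moderate confidence. No readable text adjusts the co-primaries for Visit 2 or for the stratification factors, and 3.1 and 9.1.2 conflict on whether Visit 2 enters the symptom endpoint. The conflict is visible whatever the blacked-out text contains.

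If the analysis is unadjusted, the loss is one of efficiency. There is no bias and no excess false-positive risk. At the planned 100 per arm the loss is small if the true effect is near 0.55 SD. It matters more if the effect is smaller, if many subjects are lost, or if the hyperemia analysis is restricted to a subset. These sizes rest on a back-solved effect, assumed correlations and assumed strata cut-points.

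**What to change.** 1. Reconcile Section 3.1 with 9.1.2, so that the symptom co-primary has one definition and the role of Visit 2 is explicit.
2. Before unmasking, state in 9.1.2 that each co-primary is analysed by ANCOVA of the Visit 4 value on treatment, the Visit 2 value of the same measure (the three-day mean before Visit 2 for symptoms, the study-eye grade for hyperemia) and the two IWRS stratification factors as randomised. Report the adjusted difference with its 95% confidence interval.
3. Put the same covariates in the multiple-imputation model of 9.4.
4. Use the same model for the Visit 6 secondary endpoints.
5. Keep the unadjusted t-test as a sensitivity analysis.

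The cost is wording in 9.1.2, 9.4 and the Statistical Analysis Plan. The data are already collected, and no subjects, visits or procedures are added. If the Statistical Analysis Plan already specifies such a model, 9.1.2 need only be made to match it.

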9.1.3. Analysis of Safety

Analysis of safety data will be presented for all subjects in the Safety population (i.e., all subjects receiving randomized investigational product). AEs will be coded using Medical

Dictionary for Regulatory Activities (MedDRA, most current version) and categorized by system organ class using preferred terms. AEs will be tabulated by study group with respect to their Severity and relationship to the investigational product. Ophthalmoscopy findings will be summarized descriptively. IOP measurements, BCVA and Biomicroscopy will be summarized as safety outcomes.

9.2. SAMPLE SIZE ESTIMATION

A sample size of 71 in each group will have 90% power to detect an effect size of █ using a 2-group t-test with a █ 2-sided significance level.

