Study Population:	The study population will consist of subjects with mild to moderate inflammatory MGD.
Number of Subjects:	Up to 750 subjects who are diagnosed with inflammatory MGD will be screened. From those screened, approximately 200 subjects will be randomized to KPI-121 0.25% ophthalmic suspension or vehicle.
Investigational Products:	KPI-121 0.25% ophthalmic suspension or vehicle will be supplied as investigational product.
Route and Duration of Administration:	1 to 2 drops of investigational product will be instilled in each eye four times per day (QID) for up to 30 days.
Study Design:	
This is a Phase 2, multi-center, double-masked, randomized, vehicle-controlled, parallel-group study designed to evaluate the safety and efficacy of KPI-121 0.25% ophthalmic suspension in subjects with inflammatory MGD.
 
Approximately 750 subjects will be screened and up to 200 subjects will be randomized at up to 12 centers located in the United States (US).
 
After a run-in period of treatment with vehicle, subjects will be randomized to 1 of 2 study arms in an approximate 1:1 ratio. The study arms are: 1) KPI-121 0.25% ophthalmic suspension administered as 1-2 drops in each eye QID for up to 30 days or 2) vehicle administered as 1-2 drops in each eye QID for up to 30 days.
 
Furthermore, subjects will be assigned to a study arm based on the stratification of:

- Subject's Visit 1 (Day -14) [REDACTED]
[REDACTED] AND
- Visit 1 (Day -14) investigator-rated posterior lid margin hyperemia score [REDACTED]

This study will include up to 6 clinic visits over 6 weeks. At Visit 1 Screening (14 ± 1 days prior to Day 1), subjects who meet screening inclusion/exclusion criteria will begin a 2-week run-in period during which they will be treated with 1-2 drops of single-masked vehicle in each eye QID for 14 ± 1 days.

At Visit 2 Randomization (Day 1), subjects who continue to meet inclusion/exclusion criteria (with the exception of Inclusion Criteria #4 and #7) will be eligible for randomization to KPI-121 0.25% ophthalmic suspension or vehicle.

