1.4. POPULATION TO BE STUDIED

Up to 750 subjects with mild to moderate inflammatory MGD will be screened for this study. Approximately 200 subjects will be randomized to either KPI-121 0.25% ophthalmic suspension or vehicle.

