3.3. EXPLORATORY EFFICACY ENDPOINTS

Comparison of mean investigator-rated assessment of conjunctival hyperemia between the KPI-121 0.25% ophthalmic suspension group and the vehicle group:

- Visit 4
- Visit 6

Comparison of mean investigator-rated character of the meibomian glands' contents between the KPI-121 0.25% ophthalmic suspension group and the vehicle group:

- Visit 4
- Visit 6

Comparison of mean investigator-rated expressibility of the evaluated meibomian glands between the KPI-121 0.25% ophthalmic suspension group and the vehicle group:

- Visit 4
- Visit 6

Comparison of mean corneal fluorescein staining between the KPI-121 0.25% ophthalmic suspension group and the vehicle group:

- Visit 4
- Visit 6

Comparison of mean TFBUT between the KPI-121 0.25% ophthalmic suspension group and the vehicle group:

- Visit 4
- Visit 6

Comparison of mean [REDACTED] Frequency Assessment Score between the KPI-121 0.25% ophthalmic suspension group and the vehicle group:

- Visit 4 [REDACTED]
- Visit 6 [REDACTED]

Comparison of mean change from baseline (Visit 2) in posterior lid margin hyperemia [REDACTED] for subjects with greater than or equal to a grade of 1 in at least one posterior lid margin (i.e., RUL, LUL, RLL, LLL) at Visit 2 between the KPI-121 0.25% ophthalmic suspension group and the vehicle group:

- Visit 4 as compared to Visit 2
- Visit 6 as compared to Visit 2

[REDACTED]
[REDACTED]
[REDACTED]

Comparison of mean change from baseline (Visit 2) investigator-rated assessment of conjunctival hyperemia between the KPI-121 0.25% ophthalmic suspension group and the vehicle group:

- Visit 4 as compared to Visit 2
- Visit 6 as compared to Visit 2

Comparison of mean change from baseline (Visit 2) investigator-rated assessment of the character of the meibomian glands' contents between the KPI-121 0.25% ophthalmic suspension group and the vehicle group:

- Visit 4 as compared to Visit 2
- Visit 6 as compared to Visit 2

Comparison of mean change from baseline (Visit 2) between investigator-rated assessment of the expressibility of the meibomian glands the KPI-121 0.25% ophthalmic suspension group and the vehicle group:

- Visit 4 as compared to Visit 2
- Visit 6 as compared to Visit 2

Comparison of mean change from baseline (Visit 2) corneal fluorescein staining between the KPI-121 0.25% ophthalmic suspension group and the vehicle group:

- Visit 4 as compared to Visit 2
- Visit 6 as compared to Visit 2

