9.3. LEVEL OF SIGNIFICANCE

The primary assessment of the dose-response will be evaluated using a 5% level of significance. Since both co-primary endpoints will be required to be significant at the 0.05 level, there is no adjustment needed for multiple comparisons.

All other reported *p*-values will be considered descriptive and hypothesis generating.

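### Is the trial short of power for its two-endpoint success rule because Section 9.2 powers a single t-test at 71 per group?

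*Combined protocol and SAP*

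**What the plan says.** The sample-size section of the Combined protocol and SAP (Section 9.2) is one sentence: "A sample size of 71 in each group will have 90% power to detect an effect size of" a redacted value, by a two-group t-test at a redacted two-sided level. The visible words do not say which endpoint the test is for.

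Section 9.3 sets the success rule. It sees no need for a multiplicity adjustment, reasoning: "Since both co-primary endpoints will be required to be significant at the 0.05 level".

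On the number to be randomised, Section 1.4 states: "Approximately 200 subjects will be randomized to either KPI-121 0.25% ophthalmic suspension or vehicle". Section 3.5 and the synopsis row on the number of subjects give the same approximate target. The synopsis row on study design differs: "up to 200 subjects will be randomized at up to 12 centers".

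On who is analysed, Section 9.1.2 names the ITT population, "defined as all subjects randomized, for all analyses", after which the sentence runs into a redaction. Section 9.4 provides multiple imputation for the co-primary endpoints. Section 5.3 says that withdrawn subjects are not replaced.

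**The concern.** Requiring two endpoints to succeed leaves the type I error safe but costs power. A plan that sizes one test at 90% and then demands two successes can have well under 90% power for what it is trying to show. Section 9.3 deals with the alpha side and is silent on the power side.

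The number 71 is also left hanging. Twice 71 is 142, the plan randomises about 200, and no visible sentence connects them. Dropout alone would have to be 1 − 142/200 = 29% to explain the gap, and no dropout allowance is visible. One synopsis sentence makes 200 read as a ceiling without a floor. If enrolment could properly stop near 142, the chance of meeting the trial's own success rule would be materially lower than the 90% a reader takes from Section 9.2.

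**Working it through.** **Inputs.** From the documents: 71 per group, 90% power, two-sided two-group t-test (9.2); 0.05 for each co-primary, both required (9.3); about 200 at about 1:1, so about 100 per group (1.4, 3.5). Assumed: the redacted level in 9.2 is 0.05, as in 9.3; the effect is the same on both endpoints; the within-subject correlation ρ between endpoints is 0 to 0.8, since the documents give none.

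**Step 1: the plan's own figure.** For n per group and standardised effect d, the noncentrality is d·√(n/2) on 2n − 2 degrees of freedom. The effect size is hidden, so it has to be solved from 71 and 90%. That gives d = 0.548: 0.548 × √35.5 = 3.26 against a critical value of 1.977, power 90.0%. A rounded d = 0.55 returns n = 71 with power 90.2%. The sentence is therefore consistent with a single-endpoint calculation at 0.05. Because the effect is back-solved, this is a consistency check and not an independent reproduction.

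**Step 2: power for both endpoints.** If each endpoint has power p, the power for both is the bivariate normal probability Φ₂(z, z; ρ) with z = Φ⁻¹(p). At ρ = 0 it is p².

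| Per group analysed | Each endpoint | Both, ρ = 0 | Both, ρ = 0.5 | Both, ρ = 0.8 |
|---|---|---|---|---|
| 71 | 90.0% | 81.0% | 83.2% | 85.6% |
| 87 | 94.9% | 90.0% | 91.0% | 92.3% |
| 100 | 97.1% | 94.3% | 94.8% | 95.5% |

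For example, at 100 per group: 0.548 × √50 = 3.87 against 1.972, giving 97.1%, and 0.971² = 0.943.

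**Step 3: margin.** Power of 90% for both needs 87 per group at ρ = 0, 85 at ρ = 0.5 and 81 at ρ = 0.8. Against 100 per group, 13% of subjects at ρ = 0, or 19% at ρ = 0.8, could contribute nothing before power for both falls below 90%. The 81.0% to 85.6% row describes a trial of 142, which no passage plans.

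**Step 4: sensitivity to the hidden level in 9.2.** Solve d again from 71 and 90% at another level, then test at 0.05 with 100 per group:

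| Level assumed in 9.2 | d | Both endpoints, ρ = 0 to 0.8 |
|---|---|---|
| 0.01 | 0.655 | 99.2% to 99.3% |
| 0.025 | 0.597 | 97.5% to 98.0% |
| 0.05 | 0.548 | 94.3% to 95.5% |
| 0.10 | 0.494 | 87.4% to 90.4% |

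Only a 9.2 calculation at 0.10, out of line with 9.3, brings the result below 90%, and then by less than three points.

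**Step 5: target or ceiling.** The synopsis row on the number of subjects has a ceiling of 750 screened and an approximate 200 randomised. The design row has an approximate 750 screened and a ceiling of 200 randomised. The two qualifiers look swapped in that one sentence. The other three statements of the number (the other synopsis row, 1.4 and 3.5) agree on an approximate 200.

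**The case for a change.** The strongest counter-argument is that 100 per group may not be the number analysed for hyperemia. The definition of that co-primary is redacted just before its reference to Visit 2. The exploratory hyperemia endpoint is limited to a Visit 2 subset ("for subjects with greater than or equal to a grade of 1 in at least one posterior lid margin"). Subjects are randomised after a vehicle run-in without Inclusion Criterion 4 being applied again ("with the exception of Inclusion Criteria #4 and #7) will be randomized in an approximate 1:1 ratio"). If hyperemia were tested in fewer than about 79 per group (ρ = 0) or 74 per group (ρ = 0.8), with severity tested in all 100, power for both would be below 90%. At 71 per group it would be 87.4% to 88.9%. A smaller true effect on one endpoint would also pull the joint figure down.

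This does not carry the point. The subset and its size would have to be read into blacked-out text, and blacked-out text is not missing from the plan. Four of the five parts of Inclusion Criterion 4 are hidden as well, so a reader cannot tell what hyperemia requirement, if any, is waived at Visit 2. The visible restriction belongs to an exploratory endpoint. No document figure supports unequal effects. The visible text points the other way: analysis of all randomised subjects, with imputation for the co-primaries.

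What stands is narrow. No visible sentence gives the power for both endpoints or explains why 200 was chosen, and one synopsis sentence is worded differently from the rest. A subset allowance, the two-endpoint rule or expected dropout could each account for 200; the visible text does not say which.

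**Conclusion.** No change to the plan follows. The 90% at 71 per group agrees with its own inputs, and Section 9.3 is right that requiring both endpoints needs no alpha adjustment. With about 100 per group analysed on both endpoints, alpha 0.05 and an equal effect of 0.548 SD, the chance of meeting the success rule is 94.3% to 95.5%, above the 90% quoted for one test. Carrying out the plan as written, by randomising about 200 and analysing all of them, already covers the power cost of the two-endpoint rule.

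More words in Section 9.2 would help a reader but would not alter the sample size, the analysis, the decision rule or how the result is read. The synopsis sentence that makes 200 a ceiling is a clerical slip, outweighed by three consistent statements elsewhere. The conclusion rests on the redacted level in 9.2 being 0.05, on similar effects for the two endpoints, and on hyperemia being analysed in most of those randomised. The visible text contradicts none of these.
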